12.4 Best response

The best response for each patient is determined from the sequence of objective statuses. The terminology for the five categories of objective status is identical to those that describe best response.

12.4.1 Determination of best response

The best response for each patient is determined from the sequence of objective statuses according to the following rules:

CR = at least two determinations of CR a minimum of 4 weeks apart before progression, preceded by lower statuses, or preceded, separated or followed by unknown statuses.

PR = at least two determinations of PR or better a minimum of 4 weeks apart before progression (but not qualifying for CR), preceded by lower statuses, or preceded, separated or followed by UNK statuses.

SD = at least one determination of stable disease or better

PD = a determination of progression in one of the first two assessments

UNK = the status is UNK only if all assessments before progression are UNK.

If there is a defined objective that includes the assessment/measurement of therapeutic response to the defined treatment intervention, then detailed description of the measure, methods to be used (e.g., scales and/or definitions to assess response) and the criteria to determine each level of therapeutic response should be included.

FLT-PET

Response assessment for FLT-PET will be as follows:

SUV max and average (42% threshold) for brain lesions will be measured (for FLT using summed images 45-60min). In addition, we will explore other measures such as metabolic tumor volume. For comparison, activity will also be measured in remote normal cortex and white matter. Tumor - to-normal ratios will be computed. Treatment induced changes in these parameters will be expressed as % decrease in radiotracer uptake. Tentatively, a decline by 25% [26] will be considered significant.

13.0 CRITERIA FOR REMOVAL FROM STUDY

- If the patient has a negative FLT-PET at baseline
- If the patient is no longer able to participate in the protocol and imaging schedule.
- If the patient's primary physician and the PI consider that further participation in the protocol would not be in the best interest of the patient.
- If at any time the patient is found to be ineligible for the protocol as designated in the section on Criteria for Patient/Subject Eligibility (e.g., a change in diagnosis), the patient will be removed from the study.

14.0 BIOSTATISTICS

This is a small pilot study involving 20 patients with brain metastases from breast cancer. The first cohort will include the first ten patients that are enrolled to a separate but simultaneous phase I study evaluating patients receiving concurrent sorafenib + whole brain radiotherapy (WBXRT). *The goal of the phase I study is to determine the MTD of sorafenib in breast cancer patients with brain metastases receiving WBRT.* Ten additional patients who do not enter the parallel phase I trial and receive WBXRT without sorafenib, will be consented to this imaging study. Both cohorts have the same eligibility criteria.

The first ten patients recruited into the Phase I trial of sorafenib + whole brain radiotherapy will have to agree to consent to the FLT-PET imaging study. The cohort receiving WBRT alone will be recruited independently.

The primary objective of this study is to examine radiographic response to WBRT by two modalities: FLT-PET and MRI. MRI is considered standard of care and response assessments are recorded as

CR, PR, PD, SD, and unknown (see section 12.0). FLT-PET response assessments will be recorded as SUV-MAX and a decline by 25% is considered as significant (see Section 12.0). MRI measurements will be recorded at baseline and 10 to 12 weeks post WBRT. FLT-PET measurements will be recorded at baseline, 10 days post WBXRT, and 10-12 weeks post WBXRT.

This is a small pilot study and as such, we are limited in the scope of our analyses by sample size. Data from each modality will be examined descriptively and graphically at baseline and over the course of treatment. Specifically, the distribution of response at baseline and the 10-12 week post WBXRT timepoint as assessed by MRI and FLT-PET will be examined. The median, mean, min and max of SUV max for FLT-PET will be summarized at each timepoint. Significant or nonsignificant change in SUV from baseline to the 10-12 weeks post WBRT timepoint (decline by 25%) will also be calculated and the frequency of patients with significant change will be calculated. These descriptive analyses will be done for each cohort separately. Because FLT-PET can be used to assess early treatment response, SUV values and significant SUV change from baseline to 10 days post WBRT will be examined descriptively.

As written in Section 10.1, FLT-PET imaging provides assessments in addition to SUV. These additional assessments are kinetic rate constants based on a compartmental model. These parameters will also be analyzed using the approach described above (median, mean, min and max summarize at each timepoint for each cohort). .

Based on these analyses, we will explore whether treatment response for the two modalities correlate To compare the two modalities, the proportion of patients with significant change in SUV (FLT-PET) as a dichotomous variable, will be calculated in the following two MRI response groups: CR+PR vs. PD+SD. The McNemar's test for paired samples will be done to test the agreement of the two modalities. In addition, boxplots of SUV will be graphed for each MRI response category for each cohort. Based on the literature in this patient population, there is a 65-70 percent response rate as per MRI. Median duration of response will be calculated and summarized overall and for each cohort separately.

Any clinical, tissue, or other correlations are entirely exploratory in nature. It is expected that 2 patients will be accrued per month, with accrual for all 20 patients taking approximately 1 year.

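### Early response is a stated aim of the 7-10 day FLT-PET scan, but Section 14 writes no analysis relating that scan to later MRI response

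*Combined protocol and SAP*

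**What the plan says.** **Aim.** Section 1.0 says the study will look at whether FLT-PET can establish early response, there in relation to sorafenib. Section 4.2 lists early response among the things to be determined. Section 3.5 gives early response assessment as the reason for the 7-10 day scan. Secondary objective 1 in Section 2.1 is to correlate FLT-PET response with MRI response in all patients, with no time point attached.

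**Analysis of the early scan.** Section 14.0 states that "SUV values and significant SUV change from baseline to 10 days post WBRT will be examined descriptively". The introductory clause of that sentence treats FLT-PET's ability to assess early response as given.

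**Analysis of the late scan.** Section 14.0 classifies the baseline to 10-12 week change at a 25% decline and counts the patients who meet it. Of the descriptive summaries it says: "These descriptive analyses will be done for each cohort separately".

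**Comparison with MRI.** Section 14.0 then says "the proportion of patients with significant change in SUV (FLT-PET) as a dichotomous variable, will be calculated in the following two MRI response groups", the groups being CR+PR and PD+SD. It adds: "The McNemar's test for paired samples will be done to test the agreement of the two modalities". MRI is recorded at baseline and 10-12 weeks, with none at 7-10 days.

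**Unit of measurement.** The FLT-PET part of Section 12 measures SUVmax for brain lesions, whereas Section 14.0 counts patients.

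**The concern.** A description of early SUV change shows how far uptake fell by 7-10 days. It does not show whether patients whose uptake fell early are those who respond on MRI later, which is what would make the early scan informative about response. The patient has an extra research scan and blood draw at that visit, so the analysis that uses them should be written down.

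Two missing details add to this. The interval behind the FLT-MRI table is unnamed, and nothing says how SUVmax values from several lesions become one yes or no per patient. Left open, both could be settled after the data are seen. In addition, the one test named for agreement does not measure agreement.

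**Working it through.** **1. Which FLT change meets MRI in Section 14.0**

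| Analysis | FLT interval | Set against MRI? |
|---|---|---|
| SUVmax median, mean, min, max | each time point | no |
| Count with 25% decline | baseline to 10-12 weeks | no |
| Early SUV change | baseline to 10 days | no, descriptive only |
| Proportion with significant change, McNemar's test | not named | yes |
| Boxplots of SUV by MRI category | time point not named | yes |

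The early interval is never explicitly paired with MRI. The fourth row follows on from the preceding analyses. The only change whose patient frequency is to be calculated is baseline to 10-12 weeks, which is also when the post-treatment MRI is recorded. That makes 10-12 weeks the natural reading of the unnamed interval.

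**2. What an early comparison could show**

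The plan gives no power or precision figure to reproduce; its sample size is 10 + 10 = 20. Of MRI response, Section 14.0 says "there is a 65-70 percent response rate as per MRI", without saying whether this means confirmed best response or status at 10-12 weeks. Taking it as the 10-12 week rate:

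- Responders among 20: 20 × 0.65 = 13 to 20 × 0.70 = 14, leaving 7 to 6 non-responders.
- Responders among 10: 6.5 to 7, so 6 or 7, leaving 4 or 3.

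Exact (Clopper-Pearson) 95% limits for x of n are the 0.025 quantile of Beta(x, n−x+1) and the 0.975 quantile of Beta(x+1, n−x). All numerators are assumed.

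| Setting | Early fall in MRI responders | No early fall in non-responders |
|---|---|---|
| Pooled, 13/7 | 10/13 = 77% (46-95%) | 6/7 = 86% (42-100%) |
| Pooled, 14/6 | 11/14 = 79% (49-95%) | 5/6 = 83% (36-100%) |
| One cohort, 7/3 | 5/7 = 71% (29-96%) | 2/3 = 67% (9-99%) |

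For an assumed Spearman correlation r = 0.5, the 95% CI is tanh(atanh(r) ± 1.96 × √((1 + r²/2)/(n − 3))):

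- n = 20: 0.05 to 0.78
- n = 16 (an assumed loss of four patients): −0.03 to 0.81
- n = 10: −0.23 to 0.87

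**3. How much the lesion rule can matter**

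Three or more lesions is one basis for planned WBRT in Section 6.2. Section 12.1 follows up to five measurable lesions on MRI. Assume three lesions, each with a 70% chance of a 25% fall.

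- Independent lesions: an any-lesion rule classes 1 − 0.3³ = 97.3% of patients as FLT responders; an all-lesions rule classes 0.7³ = 34.3%.
- Latent between-lesion correlation 0.8 (simulated): 82.8% and 56.2%.

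**4. McNemar's test and agreement**

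Assume 20 patients: 9 respond on both modalities, 4 on MRI only, 4 on FLT only and 3 on neither.

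- McNemar uses only the discordant pairs, 4 against 4: exact two-sided p = 1.00.
- Observed agreement = (9 + 3)/20 = 60%.
- Expected agreement = (13 × 13 + 7 × 7)/20² = 218/400 = 54.5%.
- Kappa = (0.600 − 0.545)/(1 − 0.545) = 0.12.

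The test finds no difference because the marginal rates are equal, 13/20 each, while agreement is barely above chance.

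**The case against.** The strongest reply is that the plan does what its formal objectives ask. Primary objective 2 is to examine and quantify serial FLT change, and describing the early change serves it. Section 2.1 does not list early FLT as a predictor of later MRI response, and Section 14.0 says openly that sample size limits the analyses. That much stands: the early comparison is unspecified rather than excluded, and no objective is contradicted. What survives is that Sections 1.0, 3.5 and 4.2 make early response the point of the scan, and secondary objective 1 does not confine the FLT-MRI correlation to the late time point.

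The second reply is that the interval is evident from context. It largely is, so one phrase settles it. The missing lesion rule is also mainly a matter of detail, though step 3 shows it is not negligible. The third reply is that the added tables would say little with intervals this wide. That is a fair limit on their use, but presenting them as exploratory with those intervals answers it.

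A reader might also infer that the plan promises a test of FLT's accuracy against MRI that it cannot deliver, because Section 3.5 says such a hypothesis will be tested. The documents do not support making that a defect of the analysis. Section 3.5 is background, Section 3.6 ties confirmation to tissue in an exploratory manner, Section 2.1 lists tissue as exploratory, and Section 14.0 adds: "Any clinical, tissue, or other correlations are entirely exploratory in nature". Nor is an analysis of CNS progression-free survival by FLT response missing. Section 2.1 asks only for duration of response, and Section 14.0 covers it: "Median duration of response will be calculated and summarized overall and for each cohort separately".

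**Conclusion.** The point holds in a limited form. Early response is a stated purpose of the 7-10 day scan, and Section 14.0 writes no analysis relating that scan to later MRI response. Adding one is a cheap improvement to consider, not the correction of an error that undermines the study: no stated figure is contradicted, and Section 1.0 says FLT results will not affect management. The unnamed interval and the absent lesion rule are gaps in detail. The use of McNemar's test for agreement is a mismatch of method in the comparison that is already written.

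The conclusion rests on the text. The sizes rest on assumptions: every numerator, the correlation of 0.5, the loss to n = 16, the 70% lesion rate, the between-lesion correlation, and 65-70% being the 10-12 week MRI rate.

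**What to change.** In Section 14.0:

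1. Add an exploratory comparison of the baseline to 7-10 day SUVmax change with the 10-12 week MRI. Use the 25% decline (yes/no) against objective status, and percent SUVmax change against percent change in the MRI sum of products. Label the MRI status unconfirmed, because Section 12.3 requires consecutive scans at least one month apart for CR and PR.
2. Report proportions with exact 95% CIs and the Spearman correlation, by cohort and pooled, with no confirmatory test. State how many patients lack the 10-12 week MRI and why.
3. State that the existing FLT-MRI comparison uses the baseline to 10-12 week change.
4. Fix one lesion-to-patient SUV rule in advance, preferably on the same lesions followed on MRI. A hottest-lesion rule would set one lesion against an MRI status built from up to five measurable lesions plus evaluable and new ones.
5. For both comparisons, describe agreement by the 2x2 table, percent agreement and kappa. If McNemar's test is kept for the late comparison, describe it as comparing the two response rates.

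Optional: reword Section 3.5 so that accuracy is an exploratory question addressed by tissue where available, and add a descriptive display of CNS progression-free survival by early FLT response.

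Cost: protocol text and analysis time, including matching lesions between PET/CT and MRI. No extra scans or visits are needed. The downsides are wide intervals, pooling across two differently treated cohorts, and more exploratory comparisons to report.

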1.0 PROTOCOL SUMMARY AND/OR SCHEMA

We will perform a pilot study of serial [¹⁸F] 3'-deoxy-3'-fluorothymidine (FLT) PET imaging of the brain at baseline (less than 4 weeks of initiation of WBRT), up to 7-10 days post-treatment and 10-12 weeks after treatment in patients with metastatic breast cancer to the brain (N=20) treated with standard whole brain radiotherapy (WBRT) with or without sorafenib to evaluate the radiographic response to WBRT and sorafenib. We will examine if FLT- PET imaging can be used to determine early treatment response to sorafenib. Lastly, we will also assess whether FLT can distinguish residual viable tumor from inflammation or radionecrosis. This exploratory study will include two cohorts with 10 patients each. Cohort 1 will include the first ten patients treated with WBRT concomitantly with sorafenib (The first 10 patients on [name] I "Whole Brain Radiotherapy (WBRT) with Sorafenib for Breast Cancer Brain Metastases (BCBM): A Phase I Study" will also be enrolled concurrently on this trial). Cohort 2 will include patients treated with standard WBRT alone. Patients in both cohorts will also be assessed with standard non-invasive MRI imaging of the brain in addition to [¹⁸F] FLT PET at baseline and then 10-12 weeks after completion of WBRT. MR imaging will include T1 perfusion sequence (DCE- Dynamic Contrast enhanced Perfusion MR) images. Patients will later be followed with MR imaging of the brain every 3 months (+/- 7 days) during the first year, every 6 months (+/- 7 days) thereafter until CNS progression or death. FLT PET is considered investigational, and thus these scans will be performed under an FDA-approved Investigational New Drug (IND) application. The results of the FLT scans will have no impact on patient management. On 3/26/2009 an IND (#104742) was approved for the fluorothymidine (FLT). We will cross file this IND for the use of FLT in this protocol.

Schema:

* MRI will be done within one week before FLT PET scan

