2.1 OBJECTIVES AND SCIENTIFIC AIMS

Primary Objective: The primary objectives of this study are as follows:

- 1) To examine the radiographic response to WBRT by FLT-PET and MRI for each cohort of 10 patients separately.
- 2) To examine and quantify changes in response as assessed by serial FLT PET images taken over the course of treatment for each cohort of 10 patients separately.

Secondary Objectives: The secondary objectives of this study are as follows:

- 1) To correlate treatment response as measured by FLT-PET with response assessment based on MRI of the brain in all patients and assess duration of response (i.e., CNS progression-free survival) during follow-up with MR imaging.

Exploratory Objective: The exploratory objectives of this study are as follows:

- 1) To correlate the ability of FLT-PET and MRI of the brain imaging to differentiate viable tumor, inflammation and necrosis with surgical resection specimens (if available) obtained in patients with a medical indication for craniotomy.

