3.5 Rationale for this study

Despite the treatment advances in the treatment of brain metastases, prognosis remains poor and there are no specific biomarkers available to predict response of brain metastases to available therapies. FLT-PET has been used as an imaging biomarker in patients with brain tumors to predict response to anti-angiogenic therapy. This was achieved by performing serial FLT PET imaging [21].

Following WBRT, patients often progress clinically or on MR imaging. Furthermore, radiation necrosis, a well-known phenomenon can complicate cranial radiotherapy and patients could decline quickly, often not because of disease progression in the brain, but as a result of mass effect and edema caused by necrosis [22]. Also, there is a suggestion that targeting VEGF can reduce radionecrosis by decreasing capillary leakage and the associated brain edema [23, 24] as well as potentiate the antitumor effects of external beam radiotherapy [17]. A small randomized controlled trial has shown benefit of antiangiogenic therapy for established radionecrosis [Grommes *et al. Proceedings of AAN*; 2010]. This however has not been confirmed in a well-powered randomized trial. As an antiangiogenic agent, sorafenib could potentially reduce complications of cranial radiation such as increased edema and radionecrosis. We therefore aim to explore the effect of sorafenib on the development of suspected or proven radionecrosis.

Our hypothesis is that FLT-PET will be a more accurate non-invasive biomarker than MRI in patients with metastatic breast cancer with metastases to the brain treated with WBRT with or without sorafenib. This is expected based on the higher specificity of FLT for viable residual disease. The hypothesis will be tested by having patients undergo

FLT PET and MR at baseline, FLT PET within 7-10 days after radiotherapy (for early response assessment) and again dual imaging at 10-12 weeks post WBRT.

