9.3 MR imaging of the brain

MR imaging before and after the administration of gadolinium-diethylenetriamine-pentaacetic acid (Gd-DTPA) will be obtained within 2 weeks of the PET scan. All baseline imaging scans (FLT-PET and MR Brain) will be obtained within 4 weeks prior to initiation of WBRT. MR imaging will be repeated 10-12 weeks after WBRT. MR imaging during the follow-up scan only will include the T1-Perfusion sequence (DCE) images.

FLT-PET scans are the research scans and MR imaging is considered standard of care.

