12.3 Criteria for current objective status

At each tumor assessment visit the current objective status is determined. This takes into account measurable and evaluable lesion(s). Comparisons of assessments for measurable and evaluable lesions, excluding progressive disease, are based upon major changes in tumor size on Gd-MRI scan compared to the baseline scan. The assessment is adapted from Macdonald et al. Determination of progressive disease is based upon comparison to the previous scan with the smallest measurements. Scan changes are emphasized, but are interpreted in light of steroid use and to a lesser extent, neurological findings. Categories of overall response include:

Complete response (CR): Disappearance of all enhancing tumor on consecutive MRI scans at least one month apart, off steroids and neurologically stable or improved. No new lesions may arise.

Partial response (PR): Greater than or equal to a 50% reduction (< 100%) in the sum of the products of the largest perpendicular diameters of contrast enhancement for measurable lesions and if an evaluable lesion(s) is present at baseline, no worsening for an evaluable lesion(s) on consecutive Gd-MRI scans at least one month apart, steroids stable for 72 hours prior to each scan at the same dose administered at the time of the previous scan or at a reduced dose, and neurologically stable or improved. No new lesions may arise.

Progressive disease (PD): Greater than or equal to a 25% increase in size of the product of the largest perpendicular diameters of contrast enhancement for any measurable lesions or if an evaluable(s) lesion is present at baseline, worsening for an evaluable lesion(s) or any new tumor on Gd-MRI scans or greater than or equal to 25% increase in the unidimensional measurement of the any lesion in an additional plane of axis, steroids are stable for 72 hours prior to each scan at the same dose administered at the time of the previous scan or at an increased dose, with or without neurological progression. The following will also apply:

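### The FLT-PET by MRI response table is planned only as a pool of the sorafenib and no-sorafenib cohorts, so it can show an association present in neither if sorafenib shifts both response rates

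*Combined protocol and SAP*

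**What the plan says.** Secondary objective 1 (Section 2.1) is "To correlate treatment response as measured by FLT-PET with response assessment based on MRI of the brain in all patients". Section 14.0 carries it out with one cross-table: "the proportion of patients with significant change in SUV (FLT-PET) as a dichotomous variable, will be calculated in the following two MRI response groups", the groups being CR+PR and PD+SD. FLT response is a 25% decline in SUV max. Then "The McNemar's test for paired samples will be done to test the agreement of the two modalities". Neither the table nor the test is split by cohort.

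Other analyses are split. In the same paragraph "boxplots of SUV will be graphed for each MRI response category for each cohort", and duration of response is given overall and by cohort. The by-cohort instruction earlier in Section 14.0 closes the list of single-modality summaries and comes before the cross-table, so it does not clearly reach it. Both primary objectives are also set per cohort.

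Cohort 1 comes from a phase I trial of sorafenib with WBRT and Cohort 2 receives WBRT alone. Section 15.3 says there is no randomisation.

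Three statements bear on how sorafenib could enter the table:

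- **MRI measurement.** Partial response requires a reduction of at least half in the "sum of the products of the largest perpendicular diameters of contrast enhancement for measurable lesions" (Section 12.3), with further conditions on evaluable lesions, new tumour, steroids and neurological state.
- **MRI mechanism.** Section 3.5 reports, as a suggestion, that "targeting VEGF can reduce radionecrosis by decreasing capillary leakage and the associated brain edema".
- **FLT mechanism.** Section 10.1.2 says that high-dose radiotherapy or anti-angiogenic drugs may alter how much tracer reaches the tumour, and that compartmental analysis may then have an advantage over SUV.

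**The concern.** Cohort is a treatment difference, and the protocol's own text makes it plausible that this difference acts on both variables in the table. Lesion size on MRI is measured on enhancement, which reduced leakage might affect. SUV max does not adjust for tracer delivery, which an anti-angiogenic drug might also affect. Radiotherapy is common to both cohorts; sorafenib is not.

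If Cohort 1 has more responders than Cohort 2 on both scales, pooling puts a surplus of double responders beside a surplus of double non-responders. FLT response then looks more frequent among MRI responders even when FLT says nothing about MRI response within either cohort. This is the only dichotomous comparison of the modalities and the only one with a test, so a reader would take from it whether FLT tracks MRI.

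**Working it through.** **Inputs from the documents.** Two cohorts of 10 (Section 4.2) and a literature MRI response rate of 65-70% (Section 14.0). The documents give no power, alpha or agreement figure for this comparison, so there is no stated figure to reproduce.

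**Assumptions.** All FLT response rates and the Cohort 1 MRI rates are assumed, because the documents give none. Cohort 2 MRI response is set at 65%. All 10 patients per cohort are taken as evaluable. FLT and MRI response are independent within each cohort, so the true association is zero in both.

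**Formula.** Let m1, m2 be the MRI response rates and f1, f2 the FLT response rates, with pooled means m and f. For equal cohorts:

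- pooled covariance = (m1 - m2)(f1 - f2)/4
- phi = covariance / sqrt[m(1-m) f(1-f)]

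The covariance is a product, so it is zero unless both rates differ between cohorts.

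| Case | Cohort 1 MRI/FLT | Cohort 2 MRI/FLT | Covariance | Pooled phi | FLT response in MRI responders vs non-responders |
|---|---|---|---|---|---|
| A | 90%/90% | 65%/50% | 0.25 x 0.40/4 = 0.025 | 0.131 | 73.2% vs 58.9% |
| B | 95%/90% | 65%/30% | 0.30 x 0.60/4 = 0.045 | 0.230 | 65.6% vs 37.5% |
| C | 90%/90% | 65%/65% | 0.25 x 0.25/4 = 0.0156 | 0.090 | 79.5% vs 70.6% |
| D, MRI only | 90%/65% | 65%/65% | 0 | 0 | 65% vs 65% |
| E, opposite shifts | 90%/40% | 65%/65% | -0.0156 | -0.075 | 50.5% vs 59.4% |

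Case A in full: m = 0.775, f = 0.70, and phi = 0.025/sqrt(0.775 x 0.225 x 0.70 x 0.30) = 0.025/0.1914 = 0.131.

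**Size against noise.** With no association, the standard error of phi at n = 20 is about 1/sqrt(20) = 0.22. Case A lies well within one standard error and case B is about one. In case A there are 20 x 0.225 = 4.5 expected MRI non-responders, so the 14.3-point gap amounts to 4.5 x 0.143 = 0.6 of a patient.

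**The planned test.** McNemar's test compares the two overall response rates; it does not measure association. Under the same independence, with an assumed two-sided 0.05 level and n = 20, the exact test rejects in 2.1% of trials with 65% on both scales in both cohorts, 1.4% in case C and 6.5% in case D. It therefore gives no signal of the false association in case C. Any such signal would appear only in the FLT proportions by MRI group.

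**What the by-cohort tables would hold.** Expected MRI non-responders per cohort are 10 x (1 - 0.65) = 3.5 or 10 x (1 - 0.70) = 3; pooled, 7 or 6. At the Cohort 1 rates assumed in cases A and B, the chance of no MRI non-responder among 10 is 0.90^10 = 35% or 0.95^10 = 60%, and phi in that cohort would then be undefined.

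**The case against.** The strongest reply is that this is a declared small pilot whose modality comparison is exploratory, and that the plan already gives within-cohort views: boxplots of SUV by MRI category, MRI response and frequency of FLT decline for each cohort, and Ki and k3 by cohort. A reader could see from these whether both rates differ between cohorts, which is what the confounding requires. The illustrative rates are assumptions, the resulting phi is no larger than about one standard error, and splitting leaves very few MRI non-responders. All of this stands. It limits the weight of the point, but it does not explain why the cross-table alone is left unsplit.

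A reader might go further and infer that MRI response is scored purely on enhancement, that the protocol says anti-VEGF drugs lower it, and that pooled concordance would therefore be a drug effect. The documents do not support that. Section 12 also uses evaluable lesions, new tumour, steroid dose and neurological state. Section 3.5 offers only a suggestion about leakage and edema and does not mention enhancement. An effect on MRI alone creates no association (case D). The documents also do not say whether sorafenib is still being taken at the 10-12 week scan.

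Two more inferences fail. The cross-table is not the only planned answer to the objective, because the boxplots bear on it too. And nothing in the documents makes Cohort 2 the proper main reading; the objective is set in all patients.

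**Conclusion.** The point holds in limited form. The FLT by MRI table and its test are specified once, for all patients, across two non-randomised groups that differ in sorafenib, and no by-cohort version is planned. If sorafenib shifts both response rates in the same direction, the pooled proportions can suggest an association present in neither cohort: phi of about 0.13 to 0.23 in cases A and B, less for smaller shifts, zero if only one modality shifts, and negative if they shift in opposite directions. These figures rest on assumed response rates and on independence within cohorts. They show a possible bias, not an expected one. The point concerns a secondary, exploratory comparison and is worth correcting because the correction is cheap.

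**What to change.** In Section 14.0:

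1. Report the FLT by MRI 2x2 table descriptively for each cohort, beside the pooled table.
2. State that the pooled table mixes patients treated with and without sorafenib.
3. If a combined measure of association is reported, stratify it by cohort (for example, a Mantel-Haenszel estimate).
4. Repeat the comparison with Ki and k3, which Section 10.1.2 already plans to estimate. The plan gives no response cut-off for these, so either state one in advance or summarise their change by MRI group without a cut-off.

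The cost is SAP wording and a small set of extra tables from data already planned. The drawback is sparse cells: with 3 to 3.5 expected MRI non-responders per cohort the tables are descriptive only, a cohort's own measure may be undefined, and a cohort with no MRI non-responders adds nothing to a stratified estimate.

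Separately, clarify which MRI scans include DCE. Section 1.0 says "MR imaging will include T1 perfusion sequence (DCE- Dynamic Contrast enhanced Perfusion MR) images" directly after describing MRI at baseline and at 10-12 weeks, without naming the scan. Section 9.3 says "MR imaging during the follow-up scan only will include the T1-Perfusion sequence (DCE) images", and the calendar footnote in Section 10.2 agrees with it. The sections may be compatible, but the text should say so.
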